8.7.11.1. Essential Participant Information

With reference to Local Country Prescribing Information and the ‘Participant Information and Consent Form’, Investigators must ensure that participants are fully informed regarding the following information on the hypersensitivity reaction prior to commencing ABC therapy:

- Participants must be made aware of the possibility of a hypersensitivity reaction to abacavir that may result in a life-threatening reaction or death and that the risk of a hypersensitivity reaction is increased in individuals who are *HLA-B*5701* positive.
- Participants must also be informed that *HLA-B*5701* negative individuals can also experience abacavir hypersensitivity reaction. Therefore, ANY participant who develops signs or symptoms consistent with a possible hypersensitivity reaction to abacavir MUST CONTACT their doctor IMMEDIATELY.
- Participants who are hypersensitive to abacavir should be reminded that they must never take any abacavir containing medicinal products (e.g., ZIAGEN, EPZICOM, KIVEXA, TRIZIVIR, or TRIUMEQ) again, regardless of their *HLA-B*5701* status.
- In order to avoid restarting abacavir, participants who have experienced a hypersensitivity reaction should be asked to return any remaining EPZICOM / KIVEXA tablets to the Investigator or site staff.
- Participants, who have stopped abacavir for any reason, and particularly due to possible adverse reactions or illness, must be advised to contact their doctor before restarting EPZICOM / KIVEXA as more severe symptoms may recur within hours and may include life-threatening hypotension and death.
- Each participant should be reminded to read the Package Leaflet included in the EPZICOM / KIVEXA pack. They should be reminded of the importance of removing the Alert Card included in the pack, and keeping it with them at all times.

8.7.11.2. Reporting of Hypersensitivity Reactions

If a clinically suspected case of HSR to ABC meets one of the International Conference on Harmonization ([ICH E2A](#), 1994 definitions of seriousness listed in [Section 12.4.2](#)) then, in addition to reporting the case as an SAE, the ABC HSR eCRF should also be

completed within one week of the onset of the hypersensitivity reaction. Clinically suspected cases of HSR to ABC that do not meet criteria as an SAE can be recorded as an AE.

8.7.12. Rash Without ABC HSR Symptoms

Including serious skin reactions such as Stevens-Johnson Syndrome, Toxic Epidermal Necrolysis, Erythema Multiforme or rash with significant liver dysfunction.

Participants should be instructed to contact the Investigator as soon as possible if they develop a rash on study.

Participants who develop rash of any grade should be evaluated for the possibility of an ABC HSR or a serious skin reaction such as Stevens - Johnson syndrome (SJS), Toxic Epidermal Necrolysis (TEN) or Erythema Multiforme. SJS, TEN, and Erythema Multiforme have been reported very rarely in participants taking ABC-containing products. These participants generally do not have the cluster of additional symptoms (e.g., gastrointestinal and respiratory) that characterize the ABC HSR, but they do have features typical of these serious skin reactions.

If a serious skin reaction develops, ABC (and / or all other concurrent medication(s) suspected in the Investigators causality assessment) should be discontinued, and the participant should not be re-challenged with any ABC-containing medicinal product (i.e., ZIAGEN, TRIZIVIR, EPZICOM, or KIVEXA).

As many products, other than abacavir, also cause rash and/or serious skin reactions, all other medicinal products that the participant is receiving should also be reviewed and discontinued as appropriate.

The following guidance is provided for clinical management of participants who experience rash alone in the absence of accompanying diagnosis of ABC HSR, systemic or allergic symptoms or signs of mucosal or target lesions.

CAB is an analogue of DTG and mild to moderate rash is an expected adverse reaction for DTG-containing ART. Episodes generally occur within the first 10 weeks of treatment, rarely require interruptions or discontinuations of therapy and tend to resolve within two to three weeks. No instances of serious skin reaction, including SJS, TEN and erythema multiforme, have been reported for DTG in clinical trials. For further characterization of HSR and rash observed with DTG-containing ART, please see the current version of the IB [GlaxoSmithKline Document Number [RH2009/00003/07](#)].

Rash is an adverse drug reaction (ADR) for RPV. In clinical trials, most rashes emerged during the first 4 weeks of treatment, were transient, and usually mild (Grade 1) to moderate (Grade 2). There were no Grade 4 rashes and none were serious. Treatment-related Grade 3 rash was reported in 0.1% of participants in the RPV group. Treatment-related rash led to permanent discontinuation in 0.1% of participants in the RPV group. No cases of erythema multiforme, SJS or TEN have been reported during clinical development of RPV.

Participants with an isolated Grade 1 rash may continue study drug at the Investigator's discretion. The participant should be advised to contact the Investigator immediately if there is any worsening of the rash, if any systemic signs or symptoms appear, or if mucosal involvement develops.

Participants may continue study drug for an isolated Grade 2 rash. However, study drug (and all other concurrent medication(s) suspected in the Investigators causality assessment) should be permanently discontinued for any Grade ≥ 2 rash that is associated with an increase in ALT. The participant should be advised to contact the physician immediately if rash fails to resolve (after more than 2 weeks), if there is any worsening of the rash, if any systemic signs or allergic symptoms develop, or if mucosal involvement develops.

Participants should permanently discontinue study drug [and all other concurrent medication(s) suspected in the Investigators causality assessment] for an isolated Grade 3 or 4 rash, except where the etiology of the rash has been definitively diagnosed as NOT attributable to study drug (see below), and the participant should be withdrawn from the study. Participants should be treated as clinically appropriate and followed until resolution of the AE. Every effort should be made to collect as much information as possible about the evolution of the event and any relationship with potentially related medical events (e.g., viral infection) or start of concomitant medication.

The rash and any associated symptoms should be reported as adverse events and appropriate toxicity ratings should be used to grade the events (based on DAIDS toxicity gradings – see Section 12.3, Appendix 3).

However, if the etiology of the rash has been definitively diagnosed as being unrelated to study drug and due to a specific medical event or a concomitant infection or a concomitant non-study medication, routine management should be performed and documentation of the diagnosis provided. In this situation, the study drug should be continued.

Participants in the Follow-Up Phase who are receiving ABC as part of their regimen should be evaluated for the possibility of a clinically suspected ABC HSR and managed appropriately as outlined in the local prescribing information for ABC.

Any participant receiving at least one dose of CAB LA and /or RPV LA who discontinue IP / Withdraw will initiate treatment with HAART and enter the LTFU Phase for 52 weeks of follow-up.

8.8. Pharmacokinetics

Plasma samples for determination of CAB and RPV concentrations will be collected at Day 1, Month 12 and Withdrawal visits of the study. For participants receiving oral DTG + RPV, plasma samples for determination of DTG and RPV concentrations will be collected at the Withdrawal visit of the study. Additional samples will be collected for storage during the LTFU Phase (blood and plasma). Samples (blood and plasma) for determination of RPV concentrations will be protected from light at all times, from sampling collection through analysis.

8.8.1. PK Sample Collection

Blood samples for evaluation of CAB (2 mL each), RPV (2 mL each) and DTG (2 mL each) plasma PK concentrations will be collected from Q2M and oral DTG + RPV study participants as described in [Table 5](#).

For participants transitioning from the LATTE study and receiving the CAB LA + RPV LA Q2M regimen at Day 1, PK samples should be collected within the window of 20-28 hours after the last oral dose of CAB + RPV was taken the day prior to the clinic visit. Participants will take their final dose of oral CAB + RPV in the clinic at Day 1 after the pre-dose PK sample.

These participants will be expected to complete a PK dosing diary card noting the date and time of the last three oral doses of IP prior to the scheduled clinic visits at Day 1. The information from the diary card and the actual date and time of the PK samples will be recorded in the eCRF. Additionally, dosing information on the clinic day, including dosing and the actual date and time of the PK samples, must be recorded on the eCRF.

Plasma concentrations will be summarized and used to evaluate potential exposure-response relationships.

The timing of PK samples may be altered and/or PK samples may be obtained at additional time points to ensure thorough PK monitoring.

Table 5 CAB and RPV Plasma Pharmacokinetic Sample Schedule

Participants receiving CAB LA + RPV LA Q2M injections	CAB and RPV	PK samples for storage only: Pre-dose: Day 1, Month 12, and Withdrawal LTFU Period (off-drug; storage sample) Months 1, 3, 6, 9, and 12
Participants receiving oral DTG + RPV once daily	DTG and RPV	PK samples for storage only: Withdrawal

PK window collection: All scheduled PK samples should be collected on the Day of the corresponding visit. Pre-dose samples will be taken prior to performing dosing within the clinic. Pre-dose sample collection at Day 1 (for participants transitioning from the LATTE study to Q2M dosing) should be collected 20 to 28 hours after the last oral dose of CAB and RPV was taken.

If a participant withdraws from the study a PK sample should be collected as early as practically possible (i.e., at withdrawal visit or on the day the withdrawal decision was made).

Additional details concerning handling of PK samples, labeling and shipping directions will be supplied in the central laboratory manual.

Samples for determination of RPV will be protected from light until analyzed.

8.8.2. Rationale for PK Sampling Strategy

Blood sampling for CAB, DTG and RPV concentrations will be performed during the course of the study to evaluate PK in HIV infected participants. The proposed PK visits and sampling scheme at each visit presented in Section 8.1 is based on consideration of available PK data to support interim and final PK analysis planned in this study.

8.8.3. Sample Analysis

8.8.3.1. CAB and DTG Sample Analysis

Plasma CAB and DTG analysis will be performed under the control of PTS-DMPK, GlaxoSmithKline, the details of which will be included in the SPM. Concentrations of CAB and DTG will be determined in plasma samples using the currently approved bioanalytical methodology. Raw data will be archived at the bioanalytical site (detailed in the SPM).

Once the plasma has been analyzed for CAB and DTG, any remaining plasma may be analyzed for other compound-related metabolites and the results reported under a separate GSK platform technology and science - drug metabolism and pharmacokinetics (PTS-DMPK), GSK protocol. No human deoxyribonucleic acid (DNA) analysis will be performed on these samples.

8.8.3.2. RPV Sample Analysis

Plasma RPV analysis will be performed under the control of Janssen R&D. Concentrations of RPV will be determined in plasma samples using the currently approved bioanalytical methodology. Raw data will be archived at the bioanalytical site.

Once the plasma has been analyzed for RPV any remaining plasma may be used by the sponsor for further exploratory work on pharmacokinetics, metabolites, plasma protein binding, protein analysis, and biochemistry. No human DNA analysis will be performed on these samples.

8.9. Genetics

Information regarding genetic research is included in Section 12.6, [Appendix 6: Genetic Research](#).

8.10. Viral Genotyping and Phenotyping

Whole venous blood samples will be obtained from each participant to provide peripheral blood mononuclear cells (PBMCs) and plasma for storage samples according to the Time and Events Table (see Section 8.1) for potential viral genotypic and phenotypic analyses.

Details concerning the handling, labelling and shipping of these samples will be supplied separately. Genotypic and phenotypic analyses may be carried out by Monogram Biosciences using, but not limited to, their Standard PhenoSense and GenoSure testing methods for protease (PRO), reverse transcriptase (RT), and integrase assays.

8.10.1. HIV-1 Polymerase Viral Genotyping and Phenotyping

Participants meeting confirmed virologic failure will have plasma samples tested for HIV-1 PRO and RT genotype and phenotype and HIV-1 integrase genotype and phenotype from samples collected at the time of meeting suspected virologic failure; these results will be reported to the investigator as soon as available to provide guidance for election of an alternative regimen.

[figure not shown]
8.10.2. HIV-1 Exploratory Analysis

Additional analyses for HIV-1 resistance may, for example, be carried out on PBMC samples collected at Baseline and/or on stored blood samples from other relevant time points. These analyses may include but are not limited to additional viral genotyping and/or phenotyping, as well as other virologic evaluations such as linkage and minority species analyses, low level HIV-1 RNA quantitation and measurement of viral replicative capacity. HIV-1 PRO and RT genotype and phenotype and HIV-1 integrase genotype and phenotype will also be determined on the last on-treatment isolates from participants who have HIV-1 RNA ≥ 200 c/mL regardless of confirmatory HIV-1 RNA.

8.11. Value Evidence and Outcomes

Health outcomes assessments will be conducted according to the Time and Events Table (Section 8.1). Assessments are recommended to be administered at the beginning of the visit prior to collection of blood for analysis and other scheduled assessments.

The original HIVTSQ included 10 items and underwent two stages of psychometric validation (Woodcock, 2001; Woodcock 2006). Recently, the HIVTSQ was adapted to include injectable treatment for HIV following a qualitative study with HIV participants in five European countries. The adaptation of the HIVTSQ included two additional items related to the mode of administration (ie: long acting intramuscular injection). These are:

- CCI - This section contained Clinical Outcome Assessment data collection questionnaires or indices, which are protected by third party copyright laws and therefore have been excluded.
- 

Psychometric analyses from three datasets (one from the UK, one from the USA, and one from the LATTE-2 trial) reveal that the addition of the two items in the original version of the HIVTSQ is suitable and does not reduce the overall validity of the questionnaire.

The current study will be using the HIVTSQs (status version) and the revised HIVTSQc (change version) of this recently developed HIVTSQ 12-item questionnaire. The HIVTSQ 12-item questionnaire retains the option of calculating the total score as if it only had the original 10 items (as the original 10 items are included in the HIVTSQ 12).

In addition, it allows for calculation of an 11-item scale score including the [REDACTED] item (item-[REDACTED]). The [REDACTED] item (item-[REDACTED]) will be included in the questionnaire as a stand-alone item to evaluate potentially painful injectables. These measures will assess change in treatment satisfaction over time (in the same subjects) and compare current satisfaction with previous treatment satisfaction, from an earlier time point.

The HIV Dependent Quality of Life (HIVDQoL) is an individualised, self-completion questionnaire, specifically designed to measure quality of life in people living with HIV. The HIVDQoL was based on Audit of Diabetes-Dependent Quality of Life (ADDQoL) – a widely used questionnaire designed previously for participants with diabetes and linguistically validated in more than 60 languages (Bradley, 1999; Speight, 2001, Wee, 2006). The HIVDQoL includes two overview items, 26 condition-specific domain items and a free text box. The overview items ask participants to rate their generic ‘present QoL’ (7-point Likert scale, ranging from [REDACTED] to [REDACTED]) and HIV-specific ‘impact of HIV on QoL’ (5-point Likert scale, ranging from [REDACTED] to [REDACTED]).

The “Preference” question will contain a single item exploring whether participants prefer the CAB LA + RPV LA injectable to the oral CAB + RPV regimen administered in LATTE.

The “Reason for Switch” question will contain a single item exploring the reasons why participants are interested in switching to the CAB LA + RPV LA.

8.11.1. Value Evidence and Outcomes Endpoints (Secondary)

- Change from Baseline (Day 1) in total “treatment satisfaction” score, and individual item scores of the HIVTSQs at Months 6, 12 (or Withdrawal).
- Change in treatment satisfaction over time (using the HIVTSQc) at Month 12 (or Withdrawal).
- Change from Baseline (Day 1) in HIVDQoL at Months 6, and 12, (or Withdrawal).

8.11.2. Value Evidence and Outcomes Endpoints (Exploratory)

- The “Preference” question will be assessed in participants from LATTE, to assess preference for CAB LA + RPV LA Q2M to oral CAB + RPV regimen, at Month 12 using a single dichotomous preference question.
- The “Reason for Switch” question will be administered at Day 1 (Baseline) to assess the reasons for willingness to switch to LA injectable ART.

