4.2.3. LTFU Phase – IM Regimen Only

Any participant who receives at least one dose of CAB LA and/or RPV LA and discontinues the CAB LA + RPV LA regimen for any reason must remain on suppressive HAART for at least 52 weeks after the last dose of CAB LA and/or RPV LA in order to prevent selective pressure on HIV and the potential for selection of resistant mutants.

Investigators must discuss the choice of the follow-up HAART regimen with the Medical Monitor prior to initiating the new regimen with the participant. HAART therapy should be initiated within 8 weeks after the last Q2M injection, however if withdrawn due to virologic failure, HAART should be initiated as soon as virologic

failure is confirmed. Discuss with medical monitor. The LTFU will begin the day of the last CAB LA and/or RPV LA dose and continue for 52 weeks. These participants will not complete a Withdrawal visit, but will instead move directly into the LTFU as per the Time and Events Schedule. In addition, for participants who withdraw during the LTFU, the final visit will be considered the study withdrawal visit.

Participants will be assessed with clinic visits at months 1, 3, 6, 9, and 12 during the LTFU Phase. Female participants of child bearing potential must continue to use adequate contraception methods (see Study Procedures Manual for list of accepted forms of contraception) for the entire year of follow up.

In order to assure that participants have access to HAART during the LTFU, ViiV may supply HAART regionally or reimbursement will be provided as needed during this phase. The LTFU Phase may be shortened or terminated at any time during the study for various reasons, e.g., better understanding of risks of development of resistance as CAB and RPV exposures decline, end of study timings, etc.

This phase is considered study participation and participants will be followed on study during this time. A withdrawal visit is not required for participants who do not complete the LTFU Phase. The participants' last on study visit will be considered as their withdrawal visit.

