Participants electing to receive CAB LA + RPV LA Q2M IM administration will be required to participate in clinic visits approximately every 2 months while participants electing to receive oral DTG + RPV administration will be required to participate in clinic visits approximately every 3 months. Importantly, secondary objectives of this study are to understand the acceptability, tolerability, and patient reported preferences to the novel injectable regimen. An unblinded study design supports collection of participant preference data in a way that would not be possible if a double-blind, double-dummy design were implemented. If the Q2M arm were required to receive blinded placebo tablets every day, the value of comparing safety, tolerability, and convenience of Q2M compared to oral administrations would be limited and include overly burdensome visit requirements for those randomized to Q2M administration. Additionally, the perceived value for participants to transition from the LATTE study to POLAR to receive the Q2M regimen would also be limited and may result in loss of patients with prior oral 2 drug regimen experience, thereby limiting the ability to compare and evaluate the experience gained after 6 years of treatment on an oral 2 drug regimen plus Q2M regimen administration within individual participants.

Due to the complexities, lack of feasibility and limitations of blinding CAB LA and RPV LA injections for Q2M compared to oral DTG + RPV administration, this Phase 2b study is planned as open label.

To maintain the integrity of the trial, data aggregated by actual treatment group will not be made available to members of the Study Team nor Investigators in advance of the primary analysis. Lastly, ascertainment bias affecting the primary efficacy analysis is unlikely since the primary endpoint is inherently objective, being primarily determined by HIV-1 RNA laboratory assessment. The open label design should therefore have no impact on the analysis of study endpoints.

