- Renal toxicity is met and no compelling alternate cause is identified;
- Corrected QT interval (QTc) >550 msec from three or more tracings separated by at least 5 minutes and considered causally related to IP. *Note: ECGs are not routinely conducted in this study.*
- Grade 4 clinical AE considered causally related to study drug;
- Participant has a Grade 3 or higher rash or Grade 2 rash with evidence of systemic involvement and no compelling alternative cause is identified
- Pregnancy (intrauterine), regardless of termination status of pregnancy.
- Participant withdrew consent

Efficacy data for participants withdrawing from the study will be considered evaluable up to the point at which they are withdrawn using the same criteria for evaluability as for participants who complete the study.

Safety data for all participants who receive any amount of study drug, including participants who withdraw from the study, will be included in evaluations of safety.

If a participant is prematurely or permanently withdrawn from the study, the procedures described in the Time and Events Table for the in-clinic Withdrawal visit are to be performed. An in-clinic Follow-Up visit will be conducted 4 weeks after the last dose of study medication for participants with ongoing AEs, and serious adverse events (SAEs) related & not related to study drug and also any laboratory abnormalities that are considered to be AEs or potentially harmful to the participant, at the last on-study visit.

All data from the Withdrawal visit will be recorded, as they comprise an essential evaluation that should be done prior to discharging any participant from the study.

The following actions must be taken in relation to a participant who fails to attend the clinic for a required study visit:

- a. The site must attempt to contact the participant and re-schedule the missed visit as soon as possible.

- b. The site must counsel the participant on the importance of maintaining the assigned visit schedule and ascertain whether or not the participant wishes to and/or should continue in the study.
- c. In cases where the participant is deemed ‘lost to follow up’, the investigator or designee must make every effort to regain contact with the participant (where possible, 3 telephone calls and if necessary a certified letter to the participant’s last known mailing address or local equivalent methods). These contact attempts should be documented in the participant’s medical record.

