## 9.4. Strategy for Intercurrent (Post-treatment selection) Events

No imputations would be performed for any missing data.

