#### 12.3.4. Assessment Window for Health Outcome Data

## 12.3.4.1. HIVTSQs, HIVTSQc, HIVDQoL, Preference

HIVTSQs, HIVTSQc, HIVDQoL, and Preference questionnaire assessments will be assigned to analysis visits as follows:

- 1. Baseline: Like other data, Baseline will be defined as last available recorded value up to and including the date of first Maintenance phase dose of study treatment. Baseline is not applicable for HIVTSQc and Preference assessments
- 2. Post-Baseline:
  - a. if the nominal visit identifier as captured in the source dataset corresponds to a scheduled collection per the Time and Events Schedule (see Section 12.2 and Table 11) and the assessment is collected in the Maintenance Phase (per Table 13), then the nominal visit identifier will be kept as the analysis visit.
  - b. if the nominal visit identifier is unscheduled or withdrawal, then the following procedure will be used:
    - i. Assign the assessment to a study phase according to Table 13. Proceed to step ii if the assessment is assigned to the Maintenance Phase.
    - ii. Identify the 'last nominal visit' with the HO assessment performed prior to the unscheduled/withdrawal visit to be slotted.
    - iii. The unscheduled/withdrawal visit will be slotted to the planned nominal visit subsequent to the 'last nominal visit'. If the 'last nominal visits' does not exist (e.g. no records originate from a planned nominal visit), then the unscheduled/withdrawal visit will be slot to the first planned nominal visit after Day 1.

Example 1, for HIVDQoL, the planned nominal visits are Day 1, Month 6 and Month 12. If a participant has the 'last nominal visit' (with HIVDQoL assessment) at Month 6 prior to withdrawal at Month 8, the withdrawal assessment will be slotted to the subsequent planned nominal visit of Month 12.

Example 2, for HIVDQoL, if there is unscheduled visit between Month 6 and Month 12. This unscheduled visit will be slotted to Month 12 per the rule. In this case, there are two assessments with analysis visit equal to Month 12 (i.e. the slotted value and the value at original nominal Month 12 visit). The original nominal value will be selected for summary per the rule below for multiple records—see Section 12.3.5.

Table 11 **Planned Nominal Visit of Health Outcome Data** 

Endpoints	Day 1	Month 6	Month 12
HIVTSQc			Χ
HIVTSQs	Χ	Х	Χ
HIVDQoL	Χ	Χ	Χ
Preference *			Х

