#### 12.12.9. Health Outcomes Tables

Health	Health Outcomes: Tables							
No.	Population	IDSL / Example Shell	Title	Programming Notes	Deliverable			
HIV De	pendent Qual	ity of Life (HIVD	QoL)					
6.01.	6.01. ITT-E HO_T1 Proportion of Subjects with Each Individual Questionnaire Item Score in HIVDQoL by Visit							
6.02.	ITT-E	HO_T2	Summary of HIVDQoL in Overview Items, Domain Weighted Impact Scores and Average Weighted Impact Score by Visit		M12			
6.03.	ITT-E	HO_T3	Summary of HIVDQoL Change from Baseline in Overview Items, Domain Weighted Impact Scores and Average Weighted Impact Score by Visit		M12			
HIV Tr	eatment Satis	faction Question	nnaire Status Version (HIVTSQs)					
6.04.	ITT-E	207966/primar y_02/T6.14	Proportion of Subjects with HIVTSQs - Individual Item Scores by Visit	Note: no LOCF	M12			
6.05.	ITT-E	207966/primar y_02/T6.16	Summary of HIVTSQs - Total Treatment Satisfaction Score by Visit		M12			
6.06.	ITT-E	207966/primar y_02/T6.18	Summary of HIVTSQs - Change from Baseline in Total Treatment Satisfaction Score by Visit	Note: Do not include column for prior exposure	M12			
6.07.	ITT-E	207966/primar y_02/T6.20	Summary of HIVTSQs - Change from Baseline in Individual Item Score by Visit	Note: no LOCF; do not include column for prior exposure	M12			

Health	Health Outcomes: Tables						
No.	Population	IDSL / Example Shell	Title	Programming Notes	Deliverable		
HIV Tre	eatment Satist	faction Question	naire Change Version (HIVTSQc)				
6.08.	ITT-E	207966/primar y_02/T6.23	Proportion of Subjects with HIVTSQc - Individual Item Change Score at Month 12		M12		
6.09.	ITT-E	207966/primar y_02/T6.25	Summary of HIVTSQc - Total Treatment Satisfaction Change Score at Month 12		M12		
6.10.	ITT-E	207966/primar y_02/T6.27	Summary of HIVTSQc - Individual Item Change Score at Month 12		M12		
Prefere	ence (display	for Q2M arm only	y)				
6.11.	ITT-E	207966/primar y_02/T6.38	Proportion of Subjects with Response to Each Individual Question in Preference Questionnaire at Month 12 for Subjects in Q2M	Display questions and responses per the data. Do not include footnotes [1] and [2]	M12		
Reason	Reasons for Switch (display for Q2M arm only)						
6.12.	ITT-E	207966/primar y_02/T6.41	Reasons for Switch at Baseline for Subjects from Oral CAB + RPV to Q2M	Display responses per the data.	M12		

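### Preference is asked only at Month 12, so participants who stop injections earlier are never asked, and a respondent-based percentage may overstate preference for injections

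*Protocol*

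**What the plan says.** **Timing.** Protocol 8.11.2 makes Preference an exploratory endpoint, assessed "at Month 12 using a single dichotomous preference question". In the Q2M Time and Events table (Protocol 1.3 and 8.1.1, repeated in SAP 12.2.1) its row has one mark, at Month 12, and nothing under WD. SAP Table 11 agrees.

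**The other questionnaires.** HIVTSQs, HIVTSQc and HIVDQoL are also marked under WD, and their endpoints in Protocol 8.11.1 say so. For example: "Change in treatment satisfaction over time (using the HIVTSQc) at Month 12 (or Withdrawal" (the bracket closes there).

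**What happens to those who stop injections.** Protocol 4.2.3 states: "These participants will not complete a Withdrawal visit, but will instead move directly into the LTFU". Section 7 says of premature withdrawal that "the procedures described in the Time and Events Table for the in-clinic Withdrawal visit are to be performed", and Section 7.1.5.3 asks investigators to attempt the same evaluations. A footnote to the WD column of the Q2M table gives LTFU as an alternative. The LTFU schedule (8.1.3) contains no questionnaires.

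**Analysis.** SAP 12.3.4.1 opens: "HIVTSQs, HIVTSQc, HIVDQoL, and Preference questionnaire assessments will be assigned to analysis visits as follows". Under that rule, an unscheduled or withdrawal record in the Maintenance Phase moves to the next planned visit. SAP 9.4 adds: "No imputations would be performed for any missing data". Table 6.11 is titled "Proportion of Subjects with Response to Each Individual Question in Preference Questionnaire at Month 12 for Subjects in Q2M" and is run on ITT-E. Neither SAP 9.3 nor the list of displays says whether the percentage base is all ITT-E Q2M participants or those who answered. The mock shell is not in the documents.

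**Standing of the endpoint.** Protocol 4.3 says "secondary objectives of this study are to understand the acceptability, tolerability, and patient reported preferences to the novel injectable regimen", and uses preference data to justify the open-label design. The objectives table in Section 3 lists Preference as exploratory.

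**The concern.** The question asks for a comparison of injections with the earlier oral regimen. Someone who has tried injections and given them up can answer it, and the answer is informative. Protocol 7 lists not tolerating the injections among the reasons for discontinuation, so for some participants the reason for being missing is closely tied to the outcome. With no collection after stopping and no imputation, the answers come from those still in the Q2M visit schedule at Month 12.

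At stake is how Table 6.11 can be read. Its title and population suggest the view of everyone who switched to Q2M. If the base is respondents, it gives the view of those who continued.

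**Working it through.** **1. The plan's own figures.** The documents give no expected preference rate, discontinuation rate or precision for Preference. The only precision calculation is Protocol Table 6, for the primary endpoint. At n = 100 and 3% observed, 0.03 + 1.96 × √(0.03 × 0.97/100) = 0.0634, against 6.3% stated, so it reproduces. The same formula gives a scale for Preference. At n = 100 the 95% half-width is 1.96 × √(0.9 × 0.1/100) = 5.9 points for an observed 90%, and 7.8 points for 80%. The planned 100 covers both regimens, so the Q2M group may be smaller and its interval wider.

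**2. Algebra.** Let d be the share of Q2M starters not asked, pR the share preferring injections among those asked, and pW the share among those not asked.

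- Share among all who switched: (1 − d)pR + d·pW.
- Respondent denominator: pR is reported, so the error is pR − [(1 − d)pR + d·pW] = d(pR − pW).
- Full ITT-E denominator: (1 − d)pR is reported, so the error is −d·pW, which is zero or negative.

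**3. Size with a respondent denominator (percentage points).** All three inputs are assumptions.

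| d | pR 90%, pW 0 | pR 90%, pW 45% | pR 90%, pW 90% | pR 80%, pW 0 | pR 70%, pW 0 |
|---|---|---|---|---|---|
| 1% | 0.9 | 0.45 | 0 | 0.8 | 0.7 |
| 2% | 1.8 | 0.9 | 0 | 1.6 | 1.4 |
| 5% | 4.5 | 2.25 | 0 | 4.0 | 3.5 |
| 8% | 7.2 | 3.6 | 0 | 6.4 | 5.6 |
| 10% | 9.0 | 4.5 | 0 | 8.0 | 7.0 |

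For example, at d = 5%, pR = 90% and pW = 0, the share among all who switched is 0.95 × 90% = 85.5%, and 90 − 85.5 = 4.5 points. With the full ITT-E denominator and the same d and pR, the error runs from 0 (pW = 0) to −4.5 points (pW = 90%).

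**4. A rough guide to d.** The protocol reports the LATTE-2 Q8W arm (Section 2.2 and Table 1 in 4.4.1):

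- Adverse-event withdrawals were 2% through Week 96.
- At Week 48, 115 − 106 − 8 = 1 of 115 (0.9%) had no virologic data.
- At Week 96, 115 − 108 − 5 = 2 of 115 had none. Three of the five virologic failures were lack of efficacy or withdrawal for other reasons. Together that is 5/115 = 4.3%, over 96 weeks.

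None of these is a total discontinuation rate by Month 12. They suggest that 2% to 5% is a reasonable range to show.

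**5. Would a record at stopping be used?** The only planned Preference visit is Month 12, so the slotting rule would place an eligible record there. Eligibility requires the Maintenance Phase, which SAP Table 13 ends at the LTFU ART start date. An answer given at an LTFU visit after that date would not be slotted.

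**The case against.** The strongest reply has four parts.

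- **Legitimate target.** The endpoint is defined at Month 12, and preference after a year's experience is a reasonable exploratory quantity. This stands if the table says that it describes those still on injections. Its present title and ITT-E population do not say so.
- **Denominator.** Table 6.11 names ITT-E. If percentages are taken over all ITT-E Q2M participants, no overstatement is possible. This stands in full, and is why the effect can be stated only conditionally.
- **Reasons for stopping.** Loss to follow-up, prohibited medication, virologic failure and pregnancy do not imply a dislike of injections, so pW = 0 is an extreme. This also stands. The figures at pW = 0 are upper limits.
- **Other information.** The other three questionnaires have WD entries, and SAP Tables 1.01 and 1.10 summarise why participants left. This stands in part. It shows how many left and why, but not what they preferred, and the WD entries depend on a visit that Protocol 4.2.3 says will not take place.

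Nor should SAP 12.3.4.1 be pressed too far. The rule is shared by four questionnaires and applies only if a record exists. It shows that the SAP could use a Preference answer given at stopping, not that its authors expected one.

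**Conclusion.** The gap in collection is established by the documents: before Month 12, no scheduled contact asks a participant who stops injections for a preference. The consequence is conditional. A respondent-based percentage may overstate preference by d(pR − pW). On the assumed pR = 90% and pW = 0, that is at most 1.8 points at d = 2% and 4.5 points at d = 5%, both below the 5.9-point half-width at n = 100.

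A reader might infer that the reported share is biased upward as a matter of fact. The documents do not support that. It needs a respondent denominator, which is not stated, and lower preference among stoppers, which is unknown. A reader might also measure the error on the excess over 50%, where d = 5% looks larger: (90 − 50)/(85.5 − 50) − 1 = 12.7%. Neither document uses that scale, and the figure again takes pW = 0.

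The endpoint is exploratory and descriptive, with no hypothesis attached. This is a cheap improvement to one display.

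**What to change.** 1. **Collect the answer.** Add Preference to the WD column of the Q2M schedule, asked when injections are discontinued and no later than the LTFU ART start date, so that the SAP 12.3.4.1 rule applies as written. Alternatively, extend that rule to the first LTFU visit.
2. **Reconcile the protocol.** The Synopsis and Section 4.2.3 say that those who stop injections have no Withdrawal visit. Sections 7 and 7.1.5.3 call for Withdrawal evaluations. Until these agree, a mark under WD may produce no data, for Preference or for the other three questionnaires.
3. **Specify Table 6.11.** State the denominator as all ITT-E Q2M participants and give those who discontinued before Month 12 and were not asked their own row. Anyone still on injections without an answer also needs a row, so that the rows add up. Add a sensitivity line counting those who stopped and were not asked as not preferring injections. With the full denominator, that line leaves the injection share unchanged and moves the unasked to the other side. Printing the respondent percentage beside it shows the gap.

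The cost is one existing item at discontinuation and a few lines in one table. The table changes need no new data. The downside is possibly a slightly less favourable preference figure.
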